### 13.6. PART 2 Post-Treatment Follow Up Assessments

All patients should be followed up at 3 monthly intervals (+/-2 weeks) from the end of trial treatment for 12 months or for a total of 24 months from the Part 2 pre-treatment assessment visit in case trial treatment is stopped earlier than 12 months; assessment should be in line with standard practice and should include:

- Survival and disease recurrence
- Further treatment

### Research blood sample collection:

 Research blood sample collection as specified in the PHOENIX Investigator Laboratory Manual.

A recurrence tumour tissue sample should be provided at relapse for each patient who has tissue available from a biopsy or from surgery performed routinely as part of standard patient care.

Please refer to Appendix 2 for further details on the sample collection requirements.

### 13.7. PART 2 Discontinuation from Treatment

Participants may discontinue from trial treatment at any time at their own request, or they may be discontinued at the discretion of the Principal Investigator (or delegated Co-Investigator). Reasons for discontinuation will include:

- Disease progression or recurrence
- Unacceptable toxicity
- Pregnancy
- Withdrawal of consent
- Serious non-attendance and/or persistent non-compliance with procedures defined in the trial protocol

IRAS Project Number: 249774

Participants who discontinue treatment should continue to be followed up.

# 13.8. PART 2 SCHEDULE OF ASSESSMENTS: COHORTS F & G

				Tri	ial Treatr	nent Cyc	les			End of Treatment	Post-Treatment	Follow up	
	Pre-treatment									C8 –	Discontinuation	Safety	Follow Up
			C1	C2	C3	C4	C5	C6	C7	C13	(max. 13 cycles)	Follow-up	Visits
PART 2 TRIAL ASSESSMENTS – COHORTS F & G	Day -28 to Day -1	Day -3 to Day -1	D1	D1 	D1 	At time of treatment discontinuation	30 (±7) days (and 90 [±7] days for patients receiving durvalumab) post treatment	Every 3 months (± 2 weeks) post discontinuation for 12 months					
												discontinuation	
Pre-Treatment Conditions Assessment	Х												
ECG	Х			Х	Х	Х	Х	Х	Х	Х	Х	Х	
Physical examination and vital signs 		Х		Х	Х	Х	Х	Х	Х	Х	Х	Х	
ECOG Performance Status		Х		Х	Х	Х	Х	Х	Х	Х	Х	Х	
Review of Concomitant		Х		Х	Х	Х	Х	Х	Х	Х	Х	Х	
Medication		^		^	^	^	^	^	^	^	^	^	
Safety bloods 		X		Х	Х	Х	Х	Х	X	Х	X	X	
Pregnancy test (urine or serum) 		Х		Х	х	х	х	Х	Х	х		X (30 days only)	
Review Adverse Events				Х	Х	Х	Х	Х	Х	Х	Х	Χ 6	
Assessment for any surgical complications including wound healing assessment	х												
Olaparib Administration													
(refer to Section 25: Part			X	Х	X	Х	Х	Х	X	X			
2 Olaparib & Durvalumab			D1-28	D1-28	D1-28	D1-28	D1-28	D1-28	D1-28	D1-28			
Combination Therapy)													
Durvalumab			Х	х	х	х	х	х	Х	х			
Administration (refer to			D1	D1	D1	D1	D1	D1	D1	D1			
Section 25: Part 2													

IRAS Project Number: 249774

				Tri	ial Treatn	nent Cyc	les		End of Treatment	Post-Treatment	Follow up		
	Pre-treatment		C1	C2	C3	C4	C5	C6	C7	C8 –	Discontinuation	Safety	Follow Up
			CI	CZ	CS	C4	C	CO	Č	C13	(max. 13 cycles)	Follow-up	Visits
PART 2 TRIAL ASSESSMENTS – COHORTS F & G	Day -28 to Day -1	Day -3 to Day -1	D1	D1 	D1 	D1 	At time of treatment discontinuation	30 (±7) days (and 90 [±7] days for patients receiving durvalumab) post treatment discontinuation	Every 3 months (± 2 weeks) post discontinuation for 12 months				
Olaparib & Durvalumab													
Combination Therapy )													
Dosing Compliance				Х	Х	Х	Х	Х	Х	Х	Х		
(Olaparib only)				Λ.	Λ.	^	χ	^	χ	^	Α		
Research Blood Samples for ctDNA analysis		Х		Х	Х	Х	Х	Х	Х	Х	Х		X 
Survival and further treatment follow up													Х
Disease recurrence 	Х	Х	Х	Х	Х	Х	Х	Х	Х	Х	Х	Х	Х

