#### 3.2. PART 2 - Post-Surgery Component

#### Patients allocated to Cohorts F and G

Patients allocated to Cohorts F and G during Part 1 will be provided with information relating to further trial treatment in Part 2 for discussion and at the 30-day post-surgery visit. Eligible and consenting patients will receive trial treatment for 12 months (13 cycles) in Part 2 with 4 weekly follow-up visits and serial ctDNA blood sampling.

IRAS Project Number: 249774

In all cases treatment can only commence provided that the Part 2 pre-treatment assessments confirm suitability to receive trial treatment in PART 2. Trial treatment will include olaparib and durvalumab combination therapy:

**Olaparib:** 300mg of olaparib to be administered orally twice daily on a continuous schedule Day 1-28 of each 28 days cycle.

**Durvalumab:** 1,500mg durvalumab to be administered via intravenous (IV) infusion on Day 1 only of each 28 day cycle.

For each treatment cohort a cycle consists of 28 days and planned trial treatment duration is 12 months (13 cycles) unless there is evidence of unacceptable toxicity, withdrawal of consent or if the investigator decides it is not in the best interest of the patient to continue.

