#### Patient follow-up post-discontinuation of trial treatment

Following end of trial treatment (on completion of 13 cycles or at treatment discontinuation) all patients will undergo an end of treatment visit. Safety follow-up visits will be performed 30 days (±7 days) and 90 days (±7 days) after the last dose of trial treatment. All patients will be followed up after trial treatment every 3 months (±14 days) for survival status and serial ctDNA blood sampling for up to 24 months from the Part 2 pre-treatment assessment visit.

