### **Cohorts E-G**

All patients in cohorts F and G will be given the opportunity to receive trial treatment in PART 2 provided they are confirmed suitable to commence trial treatment. Patients in cohort E will not be eligible for trial treatment in PART 2. Therefore, a maximum of 23 patients may receive trial treatment within PART 2.

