#### Footnotes:

- 1. **Cycle 2 Day 1**: Assessments should be performed as close as possible and within 3 days prior to treatment administration; trial treatment should be administered as per the above schedule, however if not possible due to unavoidable circumstances treatment may be administered 1 day prior to or delayed for up to 3 days after the due date.
- 2. **Cycle 3 Day 1 onwards:** Assessments should be performed as close as possible and within 3 days prior to treatment administration; trial treatment should be administered as per the above schedule, however if not possible due to unavoidable circumstances treatment may be administered 1 day prior to or delayed for up to 7 days after the due date.
- 3. Physical Examination and Vital Signs: To include weight, blood pressure, heart rate and temperature.
- 4. **Safety bloods:** Haematology full blood count, white cell count with differential and ANC, prothrombin time and international normalised ratio (INR); Biochemistry sodium, potassium, calcium, magnesium, ALT, gamma-glutamyl transferase (GGT), bilirubin, albumin, creatinine, alkaline phosphatase, glucose, urea. In addition for patients receiving durvalumab: TSH
- 5. **Pregnancy Test:** Women of childbearing potential should have a negative serum or urine pregnancy test within 3 days prior to commencing trial treatment within PART 2, prior to trial treatment on Day 1 of each treatment cycle and at Day 30 after last dose of trial treatment.
- 6. **Review of Adverse Events:** SAEs should be followed up until resolution.
- 7. **Research Blood Sample Collection:** Research blood samples to be collected in ctDNA preservation tubes every 3 months (+/- 2 weeks) for up to 2 years from Cycle 1 Day 1 of trial treatment in Part 2. Please refer to the PHOENIX Investigator Laboratory Manual for further instruction.
- 8. **Disease recurrence**: A recurrence tumour tissue sample should be obtained for each patient who has tissue available from a biopsy or from surgery, performed routinely as part of standard patient care

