### 17.3.3. Exploratory Endpoints Definitions

- 1. Assess the ratio change in apoptosis and tumour cell proliferation in the post-treatment biopsy compared with pre-treatment baseline biopsy.
- 2. Relationship between the primary and secondary endpoints with the mutational landscape of the treated tumour as assessed by deep sequencing of the primary and residual disease and any subsequent metastatic relapse tumour genome and of tumour ctDNA in plasma.
- 3. Descriptive relationship between changes in ctDNA in Part 2 (post surgery) compared to biomarkers response to PART 1 in all patients from cohorts B-G.
- 4. Descriptive relationship between response status in PART 1 and changes in ctDNA in PART 2 within patients from cohorts B-G identified as ctDNA positive 30 days/3 months post-surgery who receive trial treatment in PART 2.
- 5. Descriptive relationship between ctDNA mutational profile in mutated genes in ctDNA pre-treatment and post-treatment ctDNA profiles in patients in both PART 1 and PART 2.
- 6. Descriptive differences in time between ctDNA detection and time to recurrence by 2 years in both the treated groups and observation group in PART 2.
- 7. RAD51 foci and geminin scoring on pre-WOP biopsy samples
- 8. Methylation status of other HRD genes (including but not limited to BRCA2 and XRCC3) on diagnosis and pre- and post-WOP tumour samples and changes between these timepoints
- 9. Changes in phosphorylation of ataxia telangiectasia and Rad3-related protein (ATR) and its downstream effectors (including but not limited to Chk1, γH2AX, pKAP1, TAO upon drug exposure: including but not limited to levels of phosphorylation of p53, p38, p21/p27, cyclin dependent kinases (CDC25)).
- 10. Changes in biomarkers of DDR and adaptive and innate response, including but not limited to 53BP1, RAD51, RAD51C, RPA, RPA32, pRPA, BRCA1/2, PARP proteins, Shieldin complex components expression and immune checkpoint ligands and receptors and adaptive and innate immune response markers (IFNy, cGAS-STING pathway, NKG2D receptors, ligands and cell markers) in the post-treatment biopsy compared to pre-treatment baseline biopsy using gene expression profiling.

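### The follow-up column in the Section 13.8 schedule stops 12 months after discontinuation, whereas Section 13.6 follows early stoppers to 24 months; a site using the column would censor recurrence and survival early

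*Protocol*

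**What the plan says.** The planned treatment period is fixed in Section 3.2: "Eligible and consenting patients will receive trial treatment for 12 months (13 cycles) in Part 2". Follow-up after treatment is then described in several places.

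- **Section 13.8, schedule for Cohorts F and G.** The only column for post-treatment follow-up visits is headed "Every 3 months (± 2 weeks) post discontinuation for 12 months". The rows for ctDNA blood, survival and further treatment, and disease recurrence all have an entry in it.
- **Section 13.8, footnote 7 (ctDNA row only).** Samples are taken "every 3 months (+/- 2 weeks) for up to 2 years from Cycle 1 Day 1 of trial treatment in Part 2".
- **Section 13.8, other rows.** The survival and further-treatment row has no footnote. Footnote 8, on the recurrence row, deals only with providing tissue.
- **Section 13.6.** Visits are 3-monthly for 12 months from the end of treatment, or "for a total of 24 months from the Part 2 pre-treatment assessment visit in case trial treatment is stopped earlier than 12 months".
- **Section 3.2.** Survival status and ctDNA are followed "for up to 24 months from the Part 2 pre-treatment assessment visit". The Trial Summary and the treatment-site duties in Section 20.1.2 give the same horizon.
- **Section 13.7.** "Participants who discontinue treatment should continue to be followed up", with no duration.
- **Section 20.7.** The trial is expected to end once all patients have 24 months of Part 2 follow-up.

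The endpoint that uses this horizon is exploratory endpoint 6 (Sections 4.3 and 17.3.3), which describes ctDNA detection and "time to recurrence by 2 years in both the treated groups and observation group in PART 2".

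**The concern.** The heading in Section 13.8 reproduces the first limb of Section 13.6 (12 months after the end of treatment) and omits the second, which covers early stopping. The table therefore gives the intended 24 months only when treatment runs its full course.

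Sites commonly book visits from the schedule of assessments, so an incomplete heading can become practice. The patients affected would be those who stop early. Section 13.7 lists the reasons: recurrence, toxicity, pregnancy, withdrawal of consent and non-compliance. Follow-up shortened in that group alone is related to clinical course, so the censoring could not safely be treated as non-informative.

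The comparison group in endpoint 6 is not exposed in the same way. The Section 14.3 table gives fixed visits to month 24 from surgery, whatever treatment is received.

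**Working it through.** This is calendar arithmetic; no power or sample-size formula applies.

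**Inputs.** Thirteen cycles of 28 days (Section 3.2); 12 months after discontinuation (Section 13.8 heading); 24 months in total (Sections 3.2 and 13.6, footnote 7). One month is taken as 365.25 / 12 = 30.44 days.

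**Reproducing the plan's 24 months.** A completer has 13 × 28 = 364 days of treatment, and 364 / 30.44 = 11.96 months. Adding 12 gives 23.96 months, so the heading and the text agree for completers.

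**Early stopping.** If treatment stops t months after Cycle 1 Day 1, the heading ends follow-up at t + 12. The shortfall is 24 − (t + 12) = 12 − t months.

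| Stops after | t (months) | Heading ends at | Shortfall, 24 months counted from Cycle 1 Day 1 | Shortfall, counted from a visit 28 days earlier |
|---|---|---|---|---|
| first days | 0.03 | 12.0 | 12.0 | 11.1 |
| 1 cycle | 0.92 | 12.9 | 11.1 | 10.2 |
| 3 cycles | 2.76 | 14.8 | 9.2 | 8.3 |
| 6 cycles | 5.52 | 17.5 | 6.5 | 5.6 |
| 9 cycles | 8.28 | 20.3 | 3.7 | 2.8 |
| 13 cycles | 11.96 | 24.0 | 0.0 | none |

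The last column is included because Section 13.6 counts from the pre-treatment visit, and Section 13.1.1 allows some of those assessments up to 28 days before treatment. An offset of 0 to 28 days is an assumed range. It lowers each shortfall by up to 28 / 30.44 = 0.92 months, so the maximum is about 11 to 12 months.

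**Visits.** Dividing the Cycle 1 Day 1 shortfall by 3 and rounding down gives three quarterly visits lost after 1 or 3 cycles, two after 6 and one after 9.

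**Against the comparison group's clock.** The Trial Summary expects the Part 2 pre-treatment visit about 3 months after surgery. Under the heading, a treated patient is then followed to about 3 + t + 12 = 15 + t months after surgery. This is below the comparison group's 24 months whenever t is below about 9.

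**By row of the table.**

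- *ctDNA:* footnote 7 carries sampling to 2 years, so the table contradicts its own heading, but a site that reads the footnote loses no samples.
- *Survival, further treatment and recurrence:* nothing in the table corrects the heading. The conflict is with Sections 3.2 and 13.6.

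**Patients who can be affected.** Section 5.1 states that "a maximum of 23 patients may receive trial treatment within PART 2", that is 8 in Cohort F plus 15 in Cohort G.

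**The case against.** The strongest reply is that the protocol already settles the matter. Section 13.6 addresses the exact case of early stopping, Sections 3.2, 20.1.2 and 20.7 agree with it, and Section 13.7 says follow-up continues. On that view the heading is shorthand for the planned 12 + 12 months. This stands to the extent that the intended rule is clear and data are lost only where a site follows the heading instead of Section 13.6. It does not remove the conflict, because the heading is an unqualified operational instruction that gives a different answer.

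A second reply is that footnote 7 keeps patients attending every 3 months to about month 24, and recurrence and survival would be noted at the same visits. That may happen, but the footnote is attached only to the ctDNA row, and Section 3 calls the Part 2 ctDNA sampling optional for these cohorts. It cannot be relied on to carry the other rows.

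A third is that national data linkage (Sections 21.7 and 25.1.2) is a backstop. It is for vital status, though not clearly for recurrence.

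A fourth is that the stakes are small. That stands: Section 17.1.2 describes Part 2 as exploratory and descriptive, and the cohorts are not formally compared.

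A reader might go further and infer that early stoppers will lose a year of ctDNA data, or that 2-year recurrence becomes unobservable in them. The documents do not support either. Footnote 7 covers ctDNA. A patient who stopped because of recurrence has already had that event and stands to lose only later survival and further-treatment data; the others would be censored early.

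**Conclusion.** The Section 13.8 heading is wrong as written for any treated Cohort F or G patient who stops before about 12 months. If followed, it ends survival, further-treatment and recurrence follow-up 12 − t months short of the 24 months required by Section 13.6, with a maximum of about 11 to 12 months. For ctDNA the fault is only that the heading contradicts its own footnote.

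The size rests on two conditions: that a site works from the heading, and that the 24 months start at the pre-treatment visit or Cycle 1 Day 1. The consequence is early censoring, related to the reason for stopping, in exploratory endpoint 6. No primary or secondary endpoint is affected.

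At most 23 patients can be exposed. It is tempting to turn that ceiling into an expected number, but the protocol gives no rate of early stopping of Part 2 treatment. The roughly 10% in Section 1.2 is discontinuation of durvalumab monotherapy for adverse events, which is a different quantity. The contradiction does not depend on any such count.

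This is an internal inconsistency worth correcting while patients are in follow-up, because missed visits cannot be recovered.

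**What to change.** Reword the follow-up column heading in Section 13.8 to: every 3 months (± 2 weeks) until 24 months from the Part 2 pre-treatment assessment visit, regardless of when trial treatment stops. The heading then governs the survival, further-treatment and recurrence rows as well as ctDNA.

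In the same edit, use one start date for the 24 months. At present Sections 3.2 and 13.6 count from the pre-treatment visit, footnote 7 from Cycle 1 Day 1, and the Part 2 blood-sample table in Appendix 2 from the 3-month post-surgery visit. If the pre-treatment visit is kept, state which date defines it, since Section 13.1 spreads those assessments over two windows (28 days and 3 days before treatment).

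The cost is one table heading, one footnote and one row of Appendix 2. No procedure is added beyond what Section 13.6 already requires, and no treatment rule changes. Sites with patients who have already stopped early should be told of the clarification, so that remaining visits are not missed.

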#### Footnotes:

- 1. **Cycle 2 Day 1**: Assessments should be performed as close as possible and within 3 days prior to treatment administration; trial treatment should be administered as per the above schedule, however if not possible due to unavoidable circumstances treatment may be administered 1 day prior to or delayed for up to 3 days after the due date.
- 2. **Cycle 3 Day 1 onwards:** Assessments should be performed as close as possible and within 3 days prior to treatment administration; trial treatment should be administered as per the above schedule, however if not possible due to unavoidable circumstances treatment may be administered 1 day prior to or delayed for up to 7 days after the due date.
- 3. Physical Examination and Vital Signs: To include weight, blood pressure, heart rate and temperature.
- 4. **Safety bloods:** Haematology full blood count, white cell count with differential and ANC, prothrombin time and international normalised ratio (INR); Biochemistry sodium, potassium, calcium, magnesium, ALT, gamma-glutamyl transferase (GGT), bilirubin, albumin, creatinine, alkaline phosphatase, glucose, urea. In addition for patients receiving durvalumab: TSH
- 5. **Pregnancy Test:** Women of childbearing potential should have a negative serum or urine pregnancy test within 3 days prior to commencing trial treatment within PART 2, prior to trial treatment on Day 1 of each treatment cycle and at Day 30 after last dose of trial treatment.
- 6. **Review of Adverse Events:** SAEs should be followed up until resolution.
- 7. **Research Blood Sample Collection:** Research blood samples to be collected in ctDNA preservation tubes every 3 months (+/- 2 weeks) for up to 2 years from Cycle 1 Day 1 of trial treatment in Part 2. Please refer to the PHOENIX Investigator Laboratory Manual for further instruction.
- 8. **Disease recurrence**: A recurrence tumour tissue sample should be obtained for each patient who has tissue available from a biopsy or from surgery, performed routinely as part of standard patient care

# 14.PART 2 TRIAL ASSESSMENTS: Cohort E (and patients from Cohorts F & G who do not consent trial treatment in Part 2)

All patients allocated to Cohort E, and patients allocated to Cohorts F & G who did not consent to trial treatment in Part 2, should receive adjuvant treatment of physician's choice and follow-up as described in the sections below.

# 14.1. Part 2 Treatment of Physician's Choice

Patients should receive adjuvant treatment of physician's choice as clinically indicated and according to national and local guidance for dosing schedule, preparation, handling, warnings, precautions and contraindications. Treatment of physician's choice should be limited to only currently approved, and NHS available, therapies given as SOC in the trial eligible population. There are no protocol restrictions for treatment of physician's choice in terms of dose reductions permitted or treatment discontinuation, which will be based on Investigator's judgment. Details of treatment received should be documented on the appropriate eCRF within the trial database.

### 14.2. PART 2 Follow Up

All patients should be followed up as per standard guidelines, including any investigation that is deemed clinically indicated, every 3 months (+/-2 weeks), with ctDNA blood sampling, for a total of 24 months post-surgery visit.

Assessment should be in line with standard practice and should include:

- Survival and disease recurrence
- Further treatment

An assessment for any surgical complications including wound healing assessment should be performed at the 3-month post-surgery visit only.

A recurrence tumour tissue sample should be provided at relapse for each patient who has tissue available from a biopsy or from surgery, performed routinely as part of standard patient care.

### Research blood sample collection:

Research blood sample collection as specified in the PHOENIX Investigator Laboratory
 Manual

Please refer to Appendix 2 for further details on the sample collection requirements.

Please refer to Section 14 PART 2 Schedule of Assessments - Cohort E (and patients from Cohorts F & G who do not consent trial treatment in Part 2)

# 14.3. PART 2 SCHEDULE OF ASSESSMENTS : Cohort E (and patients from Cohorts F & G who do not consent trial treatment in Part 2)

PART 2 Cohort E (and patients from Cohorts F & G	PART 2 Follow-up Assessments  Months from surgery												
who do not consent trial treatment in Part 2)	3 months	6 months	9 months	12 months	15 months	18 months	21 months	24 months					
Assessments & Procedures	± 2 weeks	± 2 weeks	± 2 weeks	± 2 weeks	± 2 weeks	± 2 weeks	± 2 weeks	± 2 weeks					
Blood sample for ctDNA analysis 	Х	х	Х	Х	Х	Х	Х	х					
Assessment for any surgical complications including wound healing assessment	Х												
Survival and further treatment follow up	Х	Х	Х	Х	Х	Х	Х	Х					
Disease recurrence 	х	Х	х	Х	Х	Х	х	Х					

